8.3 Follow-up Phase

Once a subject has completed the Treatment Phase, they will enter the Post-treatment Phase. Subjects that withdraw from treatment for reasons other than progressive disease will participate in ongoing response follow-up discussed in Section 8.3.3.

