11.4.2 Adverse Event Reporting Period

All AEs, whether serious or non-serious, will be documented in the source documents from the time the signed and dated ICF is obtained until 30 days following the last dose of ibrutinib and 90 days following the last dose of MEDI4736. SAEs will be reported to the Sponsor from the time of ICF signing. Non-serious AEs will be recorded in the eCRF from the first dose of study drug until 30 days after the last dose of ibrutinib and 90 days following the last dose of MEDI4736. If both study drugs were discontinued at the same time, an SAE after 30 days and up to 90 days from the last dose of study drugs should indicate the causality for MEDI4736 only and N/A for ibrutinib (unless there is a causal relationship to ibrutinib).

SAEs reported after 30 days following the last dose of ibrutinib and 90 days following the last dose of MEDI4736 should also be reported if considered related to study drug. Resolution information after 30 days following the last dose of ibrutinib and 90 days following the last dose of MEDI4736 should be provided.

Subjects who discontinued investigational product for unacceptable AEs will be followed until there is a return to the subject's baseline condition, or until the Investigator considers that a clinically satisfactory resolution is achieved. Subjects will also be contacted to document any new onset AEs and follow any AEs that were ongoing at the time of investigational product discontinuation.

Progressive disease should NOT be reported as an event term, but instead symptoms/clinical signs of disease progression may be reported (see Section 11.1.1).

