2. GENERAL ANALYSIS CONSIDERATION

Time to event or duration of event endpoints will be based on the actual event date (or censoring date) rather than visit number or visit label. Missing efficacy or safety data will not be imputed unless otherwise specified.

In general, the baseline value is defined as the last valid measurement on or prior to the first dose of study treatment. For by-visit analysis, visit windows will be used to associate assessment with a scheduled visit and will be created in reference to the date of first dose of study treatment to assign visit number based on assessment date.

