4.2. Safety Analyses

Safety data will be summarized by tumor type cohorts. Table 2 summarizes the safety analyses to be performed for all tumor type cohorts.

Adverse events (AEs) will be coded in accordance with the Medical Dictionary for Regulatory Activities (MedDRA). Severity of AEs will be graded by the investigator according the NCI-CTCAE v4.03.

All laboratory values will be converted to and reported as international standard (SI) units. In general, only data from the central laboratory will be summarized and analyzed. Laboratory parameters will be graded using the NCI CTCAE v4.03.

Unless otherwise specified, only baseline and post-baseline values collected during the treatment-emergent period will be included in the safety analysis. A treatment-emergent adverse event is defined as any event that begins or worsens in either intensity or frequency on or after the first dose of study treatment (either ibrutinib or MEDI4736). Only treatment-emergent adverse events (TEAEs) occurring and reported during the study period will be included in the adverse event summaries. The TEAEs will be derived as those events that 1) occur after the first dose of study drug (either ibrutinib or MEDI4736), through the 30 days following the last dose of ibrutinib or 90 days following the last dose of MEDI4736 (whichever date is later); 2) any event with missing onset date and its resolution date during the treatment phase; 3) any event that is considered study drug-related regardless of the start date of the event; or 4) any event that is present at baseline but worsens in severity, seriousness, or becomes subsequently considered drug-related by the investigator.

Table 2: Summary of Safety Analyses

Safety Assessment	Definition	Analysis Methods
Safety and tolerability	
AE: TEAEs, SAEs, grade 3 or worse TEAEs, related TEAEs, TEAEs leading to treatment discontinuation, TEAEs leading to dose reduction, TEAEs leading to death, protocol- defined events of special interest, and other safety observations
 
Worst post-baseline toxicity grade for selected lab tests: Worst post-baseline toxicity grade, Hgb, creatinine clearance, abnormal uric acid, liver function abnormalities
 
Vital signs (blood pressure, heart rate, temperature, respiratory rate), and weight
	Descriptive summary statistics and/or listings

AE: adverse event; SAE: serious adverse event; TEAE: treatment-emergent adverse event

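### Some adverse events judged unrelated drop out of the all-causality tables when their onset date is missing, because the SAP's rule for them requires resolution in an undefined treatment phase

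*SAP*

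**What the plan says.** SAP section 4.2 restricts the tables: "Only treatment-emergent adverse events (TEAEs) occurring and reported during the study period will be included in the adverse event summaries". It then gives four alternative ways to qualify.

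- Item 1: the event occurs after first dose, "through the 30 days following the last dose of ibrutinib or 90 days following the last dose of MEDI4736 (whichever date is later").
- Item 2: "any event with missing onset date and its resolution date during the treatment phase".
- Item 3: "any event that is considered study drug-related regardless of the start date of the event".
- Item 4: "any event that is present at baseline but worsens in severity, seriousness, or becomes subsequently considered drug-related by the investigator".

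On missing data in general, SAP section 2 says: "Missing efficacy or safety data will not be imputed unless otherwise specified". Apart from item 2, the SAP has no rule for missing or partial adverse event dates. The protocol's own definition of a treatment-emergent event (section 10.7.1) has no rule for a missing onset date.

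The SAP does not define the treatment phase. Protocol section 8.3 separates it from follow-up: "Once a subject has completed the Treatment Phase, they will enter the Post-treatment Phase". The end-of-treatment visits at 30 days (ibrutinib) and 90 days (MEDI4736) are placed in that later phase (sections 8.3.1 and 8.3.2).

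**The concern.** Item 2 is narrower than item 1. An event with a known onset counts up to the end of the 30/90-day window. An event with no onset date must have ended, and ended in the treatment phase. Within the group that items 3 and 4 do not rescue, the rule therefore keeps events that resolved on treatment and leaves out those that did not resolve, or resolved later.

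The default also runs against what is known about these records. Protocol section 11.4.2 says: "Non-serious AEs will be recorded in the eCRF from the first dose of study drug until 30 days after the last dose of ibrutinib". A non-serious record without an onset date therefore probably describes an event on or after first dose.

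At stake are the all-causality summaries. Safety and tolerability is a primary endpoint of Phase 1b and a secondary objective of Phase 2. The study is open-label with no control arm, and Protocol section 1.3.5 reports no earlier clinical data on this combination in FL or DLBCL. Attribution is uncertain in that setting, so the all-causality tables carry much of the weight.

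**Working it through.** The plan gives no figure on this point, so the check is one of logic: apply the four items to an event whose onset date is missing. Relatedness (two levels) is crossed with end status (four levels), giving 2 × 4 = 8 kinds of event. The inputs are the four items of SAP section 4.2 and the no-imputation sentence of SAP section 2. Drug-related is taken to mean the possibly related and related categories of Protocol section 11.1.4; the SAP does not say so.

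| End status (onset missing) | Drug-related | Not drug-related, baseline worsening not shown |
|---|---|---|
| Resolved in the treatment phase | In (item 3; also item 2) | In (item 2) |
| Resolved in the 30/90-day window | In (item 3) | Out |
| Ongoing, or no end date | In (item 3) | Out |
| Fatal | In (item 3) | Out if no end date falls in the treatment phase |

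All 4 related kinds are in. Of the 4 unrelated kinds, 1 is in and 3 are out. Overall, 4 + 1 = 5 of 8 are in and 3 of 8 are out. These figures count kinds of event, not expected events.

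Two points move the count.

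1. The fatal cell is out only if the death date is not entered as the event's end date, or falls after the treatment phase. The documents do not say how the end date of a fatal event is recorded.
2. If the treatment phase were read to include the whole 30/90-day window, the second row would move in. A fatal event would then be out only if it had no end date in the window. Ongoing events and those without an end date would still be out. The count left out therefore runs from 1 to 3 of 8.

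An example shows the inconsistency with item 1. Suppose a subject takes the last dose of both drugs on day 0. The window closes on day max(0 + 30, 0 + 90) = 90. An unrelated event starts on day 45 and resolves on day 60.

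- Onset recorded: 45 ≤ 90, so item 1 counts it.
- Onset missing: day 60 lies after treatment ended, so item 2 fails. Items 3 and 4 do not apply, and the event is left out.

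The same event is classified differently only because one date is blank.

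**The case against.** The strongest reply is that the gap is narrow and mostly closed elsewhere in the same sentence. Much of this stands.

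- **Items 3 and 4 are real routes.** A reader might infer that every missing-onset event must have resolved on treatment to be counted. The text does not say that: drug-related events stay in whatever their start date, and so do worsened baseline events.
- **Late immune-related events are mostly safe.** A reader might infer that these are the ones lost. Protocol Table 4 tells investigators to regard events without a clear alternative cause as potentially immune-related, and section 11.1.4 calls an event possibly related when the drug is one of several plausible causes. Such events would be expected to enter through item 3. A DLT must be at least possibly related (Protocol section 5.3), so dose selection is not shown to be affected.
- **Deaths do not simply vanish.** An unrelated fatal event is missed only if it has no end date in the treatment phase. Protocol section 11.4.2 requires deaths within the 30/90-day periods to be reported as SAEs. SAP Table 2 lists SAEs without the treatment-emergent label and allows listings, so such an event may still be shown there. The row for fatal events in that table does carry the label.
- **Missing onset should be uncommon.** Protocol section 11.4.1 requires start and end dates for each event.

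It can also be argued that item 1 does not strictly need a recorded onset date, because non-serious events enter the eCRF only from first dose. This is less convincing. Without an onset date, the upper limit of item 1 cannot be checked. SAEs are reported from consent, so the inference does not cover them. Item 2 would also be largely redundant if missing-onset records already qualified under item 1.

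The wording of item 2 is loose enough that some may read it as requiring both dates to be missing. That is a further reason to rewrite it.

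**Conclusion.** The point holds in a limited form. Three conditions together take an event out of the all-causality summaries: it is not judged drug-related and is not a worsened baseline event; its onset date is missing; and no resolution date falls in the treatment phase. The logic follows from the text, given the reading of drug-related stated above and a treatment phase that ends before follow-up. On the broader reading of that phase the gap narrows but does not close.

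The size cannot be computed, because the documents give no rate of missing onset dates; it is probably small. One might be tempted to express each lost event as a share of 39 FL or 34 DLBCL subjects, but those are response-evaluable targets. The safety tables use all treated subjects, and a lost record changes a subject-level rate only if the subject has no other qualifying event in that row. The direction is certain: each omission from this gap can only lower a reported rate. Safety analysis is descriptive (Protocol section 10.7), so no test result is affected.

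**What to change.** Replace item 2 of the derivation in SAP section 4.2 with:

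> An event with a missing or partial onset date is treatment-emergent unless the available dates show that it ended before the first dose, began before the first dose without later worsening, or began after the later of 30 days after the last ibrutinib dose and 90 days after the last MEDI4736 dose.

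Items 1, 3 and 4 stay as they are. The new wording covers partial dates, takes the upper limit from item 1, and removes the dependence on an undefined treatment phase. It does not conflict with SAP section 2, which allows for rules specified elsewhere.

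The cost is one sentence and the matching programming, with no new data. The downside is that reported adverse event rates may rise slightly, because an event whose timing cannot be established will now be counted.

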5. MODIFICATION OF ANALYSIS TO THE PROTOCOL

Below is the major change made to the analyses in the protocol:

- The timing of interim analysis for the FL cohort is changed from “An interim analysis will be performed after 19 subjects are evaluable for tumor response after completing at least 2 response assessments” to “An interim analysis will be performed after 19 subjects are evaluable for tumor response after completing at least 1 response assessment” due to the number of early treatment discontinuations prior to 2 response assessments.
- The timing of the interim analysis for the DLBCL cohort is changed from “An interim analysis will be performed after 9 subjects are evaluable for tumor response after completing at least 2 response assessments.” to “An interim analysis will be performed after 9 subjects are evaluable for tumor response after completing at least 1 response assessment.
- Because of the substantial number of subjects who discontinued treatment due to PD after one post-baseline tumor assessment, the sponsors (Pharmacyclics and AstraZeneca) decided to hold the enrolment during the interim analysis.
- The terminology ‘Safety Assessments’ instead of ‘Safety Endpoints’ is used in Section 1.2 safety analysis part.

